Interestingly, preliminary data from our own laboratory examining the effects of a 10 minute pulse of blue-wavelength light (469 nm), using the goLITE BLU device proposed for the present study, demonstrates significant increases in brain regions involved in emotional control, alertness, and self-awareness, including the lateral prefrontal cortex, thalamus, and posterior cingulate gyrus during a conflict monitoring task (see figure).

This same cognitive task will be used as part of the proposed study during fMRI scanning. We propose that direct intervention to improve the sleep difficulties in mTBI via blue light therapy may lead to entrainment of the circadian rhythm, improved sleep, and enhancement of daytime alertness. These improvements are predicted to lead to improved emotional regulation, neurocognitive performance, and accelerated improvement in symptoms among patients with mTBI.

The primary aims of the proposed study are to examine the effectiveness of a six-week course of morning blue light therapy (MBLT) on objective and subjective measures of sleep, emotional functioning, mood, psychiatric symptom expression, and neuropsychological assessment using the most current version of the Automated Neuropsychological Assessment Metric (ANAM4) TBI battery. In addition, changes in behavioral functioning produced by MBLT will also be correlated with changes in Blood Oxygen Level Dependent (BOLD) functional magnetic resonance imaging (fMRI) during an executive control task, a virtual reality water-maze task that assesses hippocampal memory function, and a working memory n-back task. These tasks have been used extensively in our

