**Exclusion criteria:**

- Any other history of neurological illness, current DSM-IV Axis I disorder, lifetime history of psychotic disorder, or head injury with loss of consciousness > 30 minutes
- Complicating medical conditions that may influence the outcome of neuropsychological assessment or functional imaging (e.g., HIV, brain tumor, etc.)
- Abnormal visual acuity that is not corrected by contact lenses
- Metal within the body (including those made of materials considered “MRI safe,” such as permanent dental retainers or braces), claustrophobia, or other contraindications for neuroimaging (via MRI Metal Checklist)
- Less than 9th grade education
- Excess current alcohol use (more than 2 instances of intake of 5+ drinks (men) when or 4+ drinks (women) when drinking in the past two months, and/or on average drinking > 2 drinks per day (men); > 1 drinks per day (women) during the past two months (as verified via the Standard Drink handout for subjects)
- History of alcoholism or substance use disorder
- Significant use of illicit drugs

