**Functional Neuroimaging:**

Blood Oxygen Level Dependent (BOLD) functional magnetic resonance imaging (fMRI) will be collected at UAMC. Functional brain responses during cognitive challenge tasks will permit quantification of brain function changes between the MBLT and SPLT treatment groups (OBJECTIVE 2) and will be correlated with measures of sleep (OBJECTIVE 3). A Trio 3.0 Tesla whole body high-speed imaging device equipped for echo planar imaging (EPI) will be used. Head movement will be restricted using expandable foam cushions. After an automated scout image is acquired and shimming procedures performed to optimize field homogeneity, high resolution 3D MPRAGE sequences will be collected for spatial normalization, positioning the slice prescription, and for subsequent morphometric analysis (see below). Then a T1-weighted and a T2-weighted sequence will be used to gather sets of images to assist in registration of the functional data to the high-resolution anatomical scan. Functional MRI images (blood oxygenation level dependent or BOLD; Kwong et al 1992) will be acquired using a gradient echo T2\*-weighted sequence.

The following paradigms will be administered to volunteers during fMRI scanning. These tasks are visual in nature and will involve back-projection of stimuli onto a screen via a shielded LCD projector and viewed through a mirror mounted on the head coil. The three functional tasks include:

1. Multi-Source Interference Task (MSIT) (Bush & Shin, 2006): This task presents the subject with two alternating conditions. In each trial, three numbers are shown on the screen. For the control condition, subjects simply make a button press using the index, middle, or ring finger of their dominant hand to indicate the spatial location of the “number 1” on the screen (left, middle, or right). For the “interference” condition, subjects again see three numbers on the screen, but two numbers are the same and one is different. The subject must press the key that identifies the numeral (1, 2, or 3) that is different from the other two. The interference task has been shown to reliably activate the anterior cingulate gyrus in previous studies (Bush & Shin, 2006).

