**FORM: Application for Human Research**

NUMBER	FORM DATE	PAGE
F200	02/2014	31 of 39

likely preclude an individual from voluntarily gazing directly at a single diode for more than a few moments.

- 2) Participants will be informed about the potential for visual discomfort and possible hazards of long term direct staring at the diodes. This information will be listed prominently in the informed consent document and will be described orally to the participant as well.
- 3) Participants will be given a hands-on demonstration about how to use the device. During the interactive demonstration, the participant will practice the correct method for viewing and will be warned about not staring for prolonged periods at the diodes.
- 4) Participants will be given written instructions with a visual diagram outlining normal safe positioning and use of the device.

5) A warning label will also be printed and taped to the face of each device which states  
“WARNING: DO NOT STARE DIRECTLY AT THE LED SCREEN”

Participants will be instructed on proper use of the device and the importance of not looking directly at the LEDs for extended periods. Of course, individuals differ in their sensitivity to light and it is possible that unanticipated eye fatigue or irritation could occur. Direct staring at the diodes could lead to the presence of temporary afterimages. Participants will be instructed to discontinue use and contact the principal investigator immediately if any unusual sensations or discomforts are noticed.

The MR imaging procedure does not pose a significant risk to subjects meeting the entry criteria for this study. There is no known hazard associated with MR imaging. Nuclear magnetic resonance imaging does not involve ionizing radiation such as that associated with X-ray or radionuclide techniques. All studies will use radiofrequency power deposition and gradient switching which have been approved by the FDA. We do not know if MRI scanning presents a risk to unborn fetuses, so we will ask all females of childbearing potential to complete a urine pregnancy test immediately prior to the scan. This pregnancy test will be performed in the Department of Psychiatry.

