**FORM: Application for Human Research**

NUMBER	FORM DATE	PAGE
F200	02/2014	32 of 39

Participants are informed of the disturbing images at two distinct junctures during their visit: 1) During the consenting process, the experimenter mentions that some disturbing images will be shown on a screen while the participant is in the scanner, 2) The experimenter again reminds the participant that they will be asked to view some disturbing images on a screen just prior to entering the scanner. Participants are reminded at both of these times that their participation is voluntary and that they may withdraw their participation at any time and for any reason without penalty. If the participant expresses any discomfort, the experimenter will have a brief conversation about the subject's discomfort. If any indication is given from the participant that they do not feel comfortable viewing the images, their participation will be withdrawn from the study. Participants may also push a button that they are given while in the scanner to immediately stop the study if they decide upon viewing one or more images that they do not wish to continue their participation.

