**14) Monitoring the data for subject safety**

The principal investigator will oversee the collection, maintenance, and analysis of all data. The UA HSPP will be contacted immediately in the case of unexpected adverse events. This is not a treatment trial.

Additionally, a medical monitor, [name]., has been designated for this study. [name] is required to review all anticipated problems involving risk to volunteers or others, serious adverse events and all volunteer deaths associated with the protocol and provide an unbiased written report of the event to the USAMRMC Office of Research Protections (ORP) Human Research Protection Office (HRPO). At a minimum the medical monitor should comment on the outcomes of the event or problem and in the case of a serious adverse event or death comment on the relationship to participation in the study. The medical monitor should also indicate whether he/she concurs with the details of the report provided by the study investigator. Reports for events determined by either the investigator or medical monitor to be possibly or definitely related to participation and reports of events resulting in death should be promptly forwarded to HRPO.

Subjects may refuse to answer any questions that make them uncomfortable. In addition, subjects may terminate their participation in the study at any time. If significant psychopathology (e.g., threat of harm to self or others) is discovered at any time during or after a subject's visit, we will contact one of the psychiatrists on staff to determine the level of risk and establish a contract for safety. If the subject does not already have an established relationship with a psychiatrist, we will provide the appropriate referrals for psychiatric evaluation.

Assessment of MRI scanning-related safety issues will occur at every scanning session by the study staff. Risks to subjects will be minimized by following standard MRI procedures. Individual scans will be aborted if any safety parameters are breached. If the safety issue involves the patient that cannot be eliminated within the time course of the study, their involvement in the study will be terminated. If the safety issue involves the scanner or the scanning environment, no further scans will

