**FORM: Application for Human Research**

NUMBER	FORM DATE	PAGE
F200	02/2014	36 of 39

be conducted from that point, until assurances are made that all safety parameters have returned to allowable limits.

Females must have a negative pregnancy test before the MRI scan can be initiated. If the results of the pregnancy test are positive, one of the clinically trained study investigators will explain why the scan cannot be completed.

No long-lasting physical or economic harm is anticipated during scanning. Every effort will be made to reassure the patient and minimize any such discomforts while scanning. Subjects will be offered and required to wear earplugs and/or earphones to minimize the scanner noise. Subjects will be able to converse with a staff member via a microphone and speaker system at all times during the scanning session. Subjects will be provided with an emergency button to indicate an immediate concern. Subjects may ask to have a scan stopped and discontinue participation in the study at any time.

The subject may request a copy of the report or the films. If this request is made, subjects will be warned that the information released may not remain confidential.

In case of an adverse event, the principal investigator will evaluate and report such events to the UA HSPP per UA HSPP guidelines.

The diagnostic assessment and heart rate measures may reveal previously unidentified psychiatric and/or cardiac abnormalities subjects didn't know they had. If any abnormalities are identified, they will be provided with information about the finding and encouraged to follow up with their primary care physician. Subjects will be made aware that we are not providing psychiatric, neuroradiological, or other clinical services; only that we will let them know in the event that anything abnormal is noticed by the study team. We are unable to assume responsibility or offer compensation for related medical costs that they make as a result of being informed of an abnormal finding.

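### Problems confined to the scanner end the whole participation, so remaining non-imaging outcomes go uncollected after light exposure

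*Combined protocol and SAP*

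**What the plan says.** Section 14 (Monitoring the data for subject safety) assesses MRI safety at every scanning session. The first step is limited to the scan: "Individual scans will be aborted if any safety parameters are breached". If the issue lies with the participant and "cannot be eliminated within the time course of the study, their involvement in the study will be terminated", the stop becomes total. If the fault lies with the scanner or its surroundings, only scanning is suspended, until it is put right.

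Section 8 (Risks to subjects) has a second total stop, for one scanner task with distressing images: "If any indication is given from the participant that they do not feel comfortable viewing the images, their participation will be withdrawn from the study". Warnings are given at consent and again just before the scanner.

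For pregnancy, Section 8 has women of childbearing potential "complete a urine pregnancy test immediately prior to the scan". If the result is positive, Section 14 says that "one of the clinically trained study investigators will explain why the scan cannot be completed". Neither section says whether the woman then stays in the study.

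Section 1 (Background) gives the primary aims as the effect of six weeks of morning blue light on "objective and subjective measures of sleep, emotional functioning, mood, psychiatric symptom expression, and neuropsychological assessment". Imaging is introduced there as an addition.

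**The concern.** Two rules triggered by events in or just before the scanner reach past it. Nothing in the documents keeps such a person in for actigraphy, questionnaires, cognitive testing, the sleep latency test or follow-up calls, although none of these needs the magnet and most serve the primary aims.

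Before any light has been given this matters little. Afterwards, each such stop is a loss of outcome data from someone who has received an assigned treatment. The loss may also not be random. The image rule is triggered by an emotional reaction, and in healthy controls the second warning comes after the light exposure. Section 1 itself hypothesises that blue light affects mood, so these withdrawals could depend on the condition received. The biostatistical section defines no analysis set and no handling of partial data that would deal with this.

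**Working it through.** The plan gives no figure for scan-only stops. Its nearest figure is the attrition allowance in Section 5: 40 enrolled for 30 complete datasets, with about 6 (17%) lost. This does not reproduce: 30/(1 − 0.17) = 36.1, so 37, not 40; and 40 − 6 = 34, not 30. That mismatch is a separate matter and does not bear on this point. The check here is mainly textual.

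**Step 1. The stops side by side.**

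| Trigger | Section | What stops | Rest of participation |
|---|---|---|---|
| Safety parameter breached | 14 | That scan | Not ended by this step |
| Scanner or environment fault | 14 | Scanning, until resolved | Not ended |
| Positive pregnancy test | 8 and 14 | The scan | Not stated |
| Question the person finds uncomfortable | 14 | That answer | Not ended |
| Participant-related issue that cannot be eliminated | 14 | Everything | Ended |
| Not comfortable viewing the images | 8 | Everything | Ended |

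The plan therefore already uses narrow stops. The last two rows are total, and the pregnancy row is open.

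**Step 2. Timing in the main arm.** Section 7 hands out the light device at the end of the baseline assessment and scan. A stop at the first scan therefore precedes treatment and agrees with the MRI exclusions in Section 5. The relevant stop is at the second scan. By then the baseline battery, the actigraphy and diaries to that date, and the weekly Epworth scores exist. Still open are any post-treatment testing not yet done, the sleep latency test (which the post-treatment description lists last, although a list is not a schedule), the optional six weeks of actigraphy and diaries, and the one-year call with the RPCSQ, PHQ-9 and ESS.

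**Step 3. Timing in healthy controls.** Section 7 gives the order: first saliva sample, 60 minutes of light, second sample, MRI, third sample, Actiwatch issued, then a fourth sample and return of the watch at about 8:30 pm. A withdrawal at the scanner loses samples 3 and 4 and the entire Actiwatch record.

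**Step 4. Whom the image rule covers.** Section 8 words the warning for subjects in general. Section 7 introduces the scanner tasks with "The three functional tasks include" and lists MSIT, n-back and resting state, plus a food task for healthy controls only. None is described as showing distressing images. Section 2 names a BMAT and an Anticipation Task for healthy controls, but neither is described.

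**Step 5. Size of one case.** Inputs: 40 enrolled (Section 5) and half assigned to each light condition (Section 7). Per group: 40/2 = 20. One case: 1/20 = 5% of those allocated, and only for the outcomes still open in Step 2. No frequency of such events is given, so a total cannot be computed.

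**The case against.** The best defence is that exposure to these rules is narrow. MRI contraindications are excluded at entry, and the first scan precedes the lamp. The Section 14 rule needs an issue that lies with the participant and cannot be eliminated. The image rule comes after a conversation about the discomfort, and the first warning is given at consent, before any light. The healthy-control arm exists largely to supply brain targets, so a person who is not scanned contributes less. All of this stands. It limits how often the problem can arise, but it does not supply a route for the remaining outcomes when it does. In healthy controls the fourth saliva sample has a stated purpose of its own, the comparison of melatonin between active and sham light.

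A reader might infer four stronger points that the documents do not support:

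- *A positive pregnancy test stops only the scan, in contrast to other scan problems.* Section 14 is silent on participation after a positive test, and the result could itself be read as a participant issue under the termination rule. This is an ambiguity, not two opposite rules.
- *Outcomes are discarded.* The text ends future involvement. Nothing deletes or excludes data already collected.
- *Each case costs 1/15 = 6.7% of an arm on every non-imaging outcome.* The 15 are completers after attrition. A terminated participant comes from about 20 allocated, and much has been collected by the second scan.
- *Claustrophobia at the second scan triggers termination.* Section 8 treats anxiety in the enclosed space as discomfort, and Section 14 meets discomfort with reassurance and the right to stop a scan.

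That the image rule deters people from voicing discomfort is conjecture. The position of the image warning, next to the EEG/EKG and saliva items, suggests the healthy-control arm, but the text does not say so.

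**Conclusion.** The concern holds in a limited form. As written, two scanner-specific rules end all participation, and after light exposure this leaves uncollected the outcomes listed in Steps 2 and 3. The statement on pregnancy leaves the same question open.

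One main-arm case is about 5% of a group, assuming equal allocation of 40 and counting only outcomes not yet collected. The number of cases, and so the total loss, cannot be estimated. That the losses depend on the light condition is a possibility arising from the plan's own mood hypothesis, not something shown. Whether the safety criteria themselves are right is not judged here. With a target of 30 complete datasets, an avoidable loss of treated participants is worth preventing.

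**What to change.** Reconcile the image rule in Section 8 with the termination and pregnancy statements in Section 14, so that the plan separates ending a scan or image task from ending outcome collection. For participants already randomised or exposed, provide for collecting the remaining non-imaging outcomes with their consent, and state that these participants are analysed with the non-imaging data available. State what happens to participation after a positive pregnancy test. Name the image task and the arm it applies to. The safety criteria for stopping a scan, and whether light use continues in a given case, are for the investigators.

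The cost is protocol and consent wording. Imaging analyses will have slightly fewer cases than non-imaging analyses, and the two sets of numbers should be reported separately.

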**FORM: Application for Human Research**

NUMBER	FORM DATE	PAGE
F200	02/2014	36 of 39

be conducted from that point, until assurances are made that all safety parameters have returned to allowable limits.

Females must have a negative pregnancy test before the MRI scan can be initiated. If the results of the pregnancy test are positive, one of the clinically trained study investigators will explain why the scan cannot be completed.

No long-lasting physical or economic harm is anticipated during scanning. Every effort will be made to reassure the patient and minimize any such discomforts while scanning. Subjects will be offered and required to wear earplugs and/or earphones to minimize the scanner noise. Subjects will be able to converse with a staff member via a microphone and speaker system at all times during the scanning session. Subjects will be provided with an emergency button to indicate an immediate concern. Subjects may ask to have a scan stopped and discontinue participation in the study at any time.

The subject may request a copy of the report or the films. If this request is made, subjects will be warned that the information released may not remain confidential.

In case of an adverse event, the principal investigator will evaluate and report such events to the UA HSPP per UA HSPP guidelines.

The diagnostic assessment and heart rate measures may reveal previously unidentified psychiatric and/or cardiac abnormalities subjects didn't know they had. If any abnormalities are identified, they will be provided with information about the finding and encouraged to follow up with their primary care physician. Subjects will be made aware that we are not providing psychiatric, neuroradiological, or other clinical services; only that we will let them know in the event that anything abnormal is noticed by the study team. We are unable to assume responsibility or offer compensation for related medical costs that they make as a result of being informed of an abnormal finding.

There may be instances in which an abnormality exists but is not identified in our analyses. Our team is not trained in clinically diagnosing issues pertaining to abnormalities found in the collected data. Further, our data analyses are not intended to treat, diagnose, or replace the expertise of a medical doctor or a medical diagnosis. Thus, they should not rely on our analyses to reveal abnormalities in your data, and our lab claims no responsibility for abnormalities that go undetected during their participation in any research related activities.

